13.4 Combined Solicited and Unsolicited Adverse Events

A summary of subjects with all combined solicited (regardless of their duration) and unsolicited adverse events will be provided. Solicited adverse events will be coded by MedDRA. For clintrial.gov and EudraCT posting purposes, a summary of combined solicited and unsolicited non-serious adverse events will be produced by System Organ Class and according to occurrence of each event. A further differentiation of combined adverse events according to seriousness, severity, or relationship is not performed.

13.5 Clinical Safety Laboratory Investigations

Clinical safety laboratory values, and change-from-baseline values (day x to day 1), will be summarized (mean, standard deviation, median, minimum and maximum) at each time-point of assessment, by vaccine group, for the subset of subjects in the Overall Safety Set with available laboratory data.

The frequencies of subjects with clinical laboratory values below, within, or above normal ranges will be tabulated for each clinical laboratory variable by vaccine-group and time-point of assessment (3 x 3 shift tables).

A summary of clinically significant laboratory abnormalities by time point will be provided.

Laboratory values that are outside the normal range will also be flagged in the data listings, along with corresponding normal ranges and assessment of clinical significance.

For subjects presenting at least one clinically significant value, an additional listing will be provided of all laboratory results by vaccine group, by subject, and by relevant parameter. Clinical significance assessed by the investigator will be presented.

13.6 Concomitant Medication

The frequencies and percentages of subjects reporting concomitant medications will be tabulated overall and by vaccine group. Medications (generic drug name) will be coded using the WHODRUG dictionary (see [section 8.7](#) for definition).

14. INTERIM ANALYSIS

14.1 Interim Analysis

There are no planned interim analyses for this study.

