8.3.6 Other Analysis Sets

Modified FAS

The differences between FAS and Modified FAS are:

- Subjects who received the same wrong vaccine at the two vaccinations will be analyzed in the vaccine the subject actually received (in the FAS they will be analyzed according to the vaccine the subject was designed to receive)
- If a subject didn't receive the vaccination but a blood sample after the vaccination visit (where subject didn't receive the vaccination) was collected then subject will be excluded from the immunogenicity analysis for all visits after the vaccination visit.

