8.4.3.3.2 Analysis Sets

The modified FAS will be the primary analysis set for the immunogenicity objective.

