8.6 Interim Analysis

For up to 45 subjects, once they have completed the study, a group unblinded preliminary immunogenicity analysis and a blinded interim safety analysis will be performed. Individual subject results from preliminary analyses will not be made available to site and sponsor personnel until the end of the study. The results of these immunogenicity and safety analyses will not impact the conduct of the study, but will inform the planning of future studies with the same vaccine.

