Prior to unblinding, designated GVGH staff will develop a memo that describes the PDs that led to exclusions from analysis sets. This memo will be signed off by at least the Biostatistician and the Physician and will be included in the trial master file (Exclusion Memo).

Prematurely terminating study participation for reasons such as withdrawal of consent or occurrence of adverse events (including death) is not considered as a PD. The missing assessments that should have otherwise been collected for that subject later in the study are also not considered as a PD.

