7.6 Other Analysis Set

Modified FAS

The difference between FAS and Modified FAS are:

Subjects who received a wrong vaccine at both vaccinations will be analyzed in the vaccine the subject actually received (in the FAS they will be analyzed according to the vaccine the subject was designed to receive)

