15. DATA MONITORING COMMITTEES

Follow the GVGH departmental SOPs (PHV 2502) and regulatory agency guidance documents on data monitoring committees.

Refer to the study specific DSMB charter if applicable, for further details on interim analysis.

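### The SAP does not match protocol version 4.0 on the interim analysis, the missed-vaccination rule of the modified FAS, or FAS membership of mis-vaccinated subjects

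*SAP*

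**What the plan says.** **Interim analysis.** Protocol section 8.6, as changed by Amendment 3, plans the following: "For up to 45 subjects, once they have completed the study, a group unblinded preliminary immunogenicity analysis and a blinded interim safety analysis". SAP section 14.1 states "There are no planned interim analyses for this study". The only other mention in the SAP is in section 15: "Refer to the study specific DSMB charter if applicable, for further details on interim analysis". On the timing of exclusions, SAP section 6.1 says "Prior to unblinding, designated GVGH staff will develop a memo that describes the PDs that led to exclusions from analysis sets".

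**Modified FAS.** Protocol section 8.4.3.3.2 fixes its role: "The modified FAS will be the primary analysis set for the immunogenicity objective". SAP section 8.2.2 agrees. Protocol section 8.3.6 lists two differences from the FAS. One concerns a subject who skips a vaccination but is bled afterwards: that "subject will be excluded from the immunogenicity analysis for all visits after the vaccination visit". The other is reassignment: "Subjects who received the same wrong vaccine at the two vaccinations will be analyzed in the vaccine the subject actually received". SAP section 7.6 has reassignment only, worded differently: "Subjects who received a wrong vaccine at both vaccinations will be analyzed in the vaccine the subject actually received".

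**FAS.** Protocol section 8.3.4 and SAP section 7.3 analyse subjects with a vaccination error as randomized. SAP section 4.1.1 says the same of misrandomizations, which it excludes from the PPS only. SAP Table 7.7-2 marks codes 120 and 120.2 as excluded from FAS 1 and FAS 2 as well.

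**The concern.** Analysis-set flags are normally programmed from the SAP. Programmed from this one, they would not reproduce the protocol's sets. Post-dose-2 GMCs, GMRs and seroresponse rates could include subjects never given dose 2. Mis-vaccinated subjects would leave a FAS that both documents say retains them. Because the modified FAS is defined only by how it differs from the FAS, that error could carry into the primary immunogenicity set.

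The interim look adds a timing problem. The SAP settles exclusions before unblinding but does not say whether the group-unblinded look counts as that unblinding. Exclusions for the interim cohort could therefore be decided after group results are known.

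No hypothesis is tested, so no type I error is at stake. What is at stake is whether the sets are correct and reproducible.

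**Working it through.** The documents attach no figure to these points, so the check is mainly a comparison of texts, followed by a bound on the effect.

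**1. Interim.** Protocol 8.6 says the analysis will be done; SAP 14.1 says none is planned; SAP 15 is a conditional pointer to the DSMB charter and describes nothing. Cohort ceiling: 45/72 = 62.5% of subjects, or 45/3 = 15 per arm if the first completers happen to be balanced.

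**2. Missed-vaccination rule.** Nothing else in the SAP supplies it:
- FAS 2 (SAP 7.3) asks for at least one vaccination plus serology at the post-dose-2 time point.
- In Table 7.7-2, code 140.5 (incomplete series) excludes from the PPS columns only, and code 260.2 (second dose not done or out of window) from PPS 2 only.
- Code 110.5 removes a subject from FAS 2 only when Visit 5 serology is missing.
- The table has no modified FAS column.

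Protocol 8.3.6 states the rule as a difference from the FAS, so the FAS itself does not contain it. Protocol 3.9 encourages subjects withdrawn from vaccination to stay until the termination visit, so Visit 5 samples without dose 2 can arise.

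**3. Reassignment wording.** The control regimen is two products (protocol 3.1). A subject wrongly given Menveo and then Boostrix did not receive one wrong vaccine twice, so the protocol wording read literally misses that subject. The SAP wording covers it.

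**4. Table 7.7-2.** It has six set columns: All Exposed, FAS 1, FAS 2 and three PPS columns. Code 130 carries three exclusion marks, all PPS, as SAP 4.2 requires. Code 120.2 carries five; 5 − 3 = 2 extra marks, which fall on FAS 1 and FAS 2. A shifted table cannot explain this, because only four columns are not FAS columns and five marks must therefore hit at least one. Code 120 carries six marks and so covers both FAS columns.

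**5. Size of point 2.** Assume *k* of *n* subjects in an arm lack dose 2 but have a Visit 5 sample, and that dose 2 multiplies titre by *r*. The mean log titre falls by (*k*/*n*)·log *r*, so the GMC falls by 1 − *r*^(−*k*/*n*):

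| | n = 24 | n = 20 |
|---|---|---|
| k = 1, r = 1.5 | 1.7% | 2.0% |
| k = 1, r = 2 | 2.8% | 3.4% |
| k = 2, r = 1.5 | 3.3% | 4.0% |
| k = 2, r = 2 | 5.6% | 6.7% |

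For comparison, the 95% CI half-width in log10 is t(0.975, n−1)·SD/√n. With an assumed SD of 0.3 to 0.5:
- n = 24: 0.127 to 0.211, so the lower limit lies 25% to 39% below the GMC.
- n = 20: 0.140 to 0.234, so it lies 28% to 42% below.

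Seroresponse, worst case (every subject given dose 2 responds, the others do not), at n = 24:
- One such subject: 23/24 = 95.8% (Clopper-Pearson 78.9 to 99.9), against 23/23 = 100% (85.2 to 100) with the rule applied.
- Two: 22/24 = 91.7% (73.0 to 99.0), against 22/22 = 100% (84.6 to 100).

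The fall is 4.2 to 8.3 points, and can be zero if dose 1 already produced a seroresponse.

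**6. Size of point 4.** Each mis-vaccinated subject dropped is 1/24 = 4.2% of an arm.

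**The case against.** - **The interim mismatch may be only an SAP not yet updated.** SAP 14.1 agrees with the protocol as it stood before Amendment 3, the SAP's date is not visible, and the Amendment 3 form marks the SAP for revision. Protocol 8.6 adds that the look will not affect conduct and that individual results are withheld. This may explain the gap but does not close it. It cannot explain the other two points, because both rules were already in protocol version 1.0.
- **FAS 2 can be read as requiring dose 2**, since its time point is counted from the second vaccination. That reading is possible, but it would leave the protocol's stated difference between the two sets without effect.
- **Few such samples may exist.** Protocol 5.5.1 bars immunogenicity blood at an early termination visit unless the sponsor agrees beforehand. This stands, and it limits the size of the effect.
- **Code 120 is labelled randomization failure**, which protocol 5.1.4 uses for subjects never randomized. But SAP 4.1.1 and 6.1 use code 120 for vaccination not matching randomization, and code 100 already removes the never-vaccinated. The clash of terms should be cleared up.
- **Code 120.2 covers only first-dose errors, and the main analysis uses the modified FAS.** Both are true. But a subject given a wrong vaccine at both visits also had a first-dose error, so the table would remove from the FAS the very subjects that SAP 7.6 reassigns.
- **The Menveo and Boostrix point faults the protocol, not the SAP.** That is correct; the two wordings still need to be reconciled.

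**Conclusion.** All three departures stand. The interim and missed-vaccination points are differences between the SAP and the protocol; the FAS exclusion also contradicts the SAP's own text. They should be corrected, because sets built from SAP section 7.6 and Table 7.7-2 as written would be wrong.

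The likely numerical effect is small: a GMC shift of 1.7% to 6.7%, at most 8.3 percentage points on seroresponse, and 4.2% of an arm for each mis-vaccinated subject dropped. The GMC and seroresponse figures rest on an assumed one or two affected subjects per arm; the GMC range also assumes a 1.5 to 2 fold effect of dose 2, and its comparison with sampling error assumes a log10 SD of 0.3 to 0.5. None of these values is in the documents. The mark for code 120 under All Exposed may be a table-reading artefact and is not counted as an error.

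**What to change.** 1. Describe the protocol 8.6 analysis in SAP section 14. Require deviations and exclusions for the interim cohort to be settled and documented before the group unblinding, with any later change documented and justified.
2. Restore the missed-vaccination rule in SAP 7.6 and give the modified FAS its own column in Table 7.7-2.
3. Use one reassignment rule in both documents, based on the regimen actually received over both visits, so that Menveo followed by Boostrix counts as the control regimen.
4. In Table 7.7-2, remove the FAS 1 and FAS 2 exclusions for codes 120 and 120.2 and keep those for the PPS. Relabel code 120 so that it cannot be confused with the term in protocol 5.1.4, and check its All Exposed cell against the original table.

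The cost is SAP wording and table cells, plus a one-line alignment of protocol 8.3.6 if its reassignment wording is to match. No new data or procedures are needed, and Amendment 3 already calls for an SAP revision.

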14.1.1 Futility Analysis

Not Applicable.

15. DATA MONITORING COMMITTEES

Follow the GVGH departmental SOPs (PHV 2502) and regulatory agency guidance documents on data monitoring committees.

Refer to the study specific DSMB charter if applicable, for further details on interim analysis.

16. PEER REVIEW

Peer review of analyses should be performed in accordance with the applicable procedures for validation of SAS programs used in clinical data analysis (see BCDM-17).

The following analyses are identified in the PID as key analyses to be peer reviewed by a biostatistician independent from the study:

- Immunogenicity analysis.

The programs to be peer reviewed by a second SP will be identified in the PID.

17. LIST OF FINAL REPORT TABLES, LISTINGS AND FIGURES

For the complete list of tables, listings and figures, please refer to the Table of Contents (TOC). Note that a listing of individual efficacy/immunogenicity lab data (see “Other TOC” tab in the TOC) will be created, to allow data dissemination to the study subjects. This listing will show the following data:

- Subject ID
- Actual vaccine(s) received by the subject
- Lab results for immunogenicity safety at each visit.

This listing is mentioned in the tab “Other TOC” in the TOC and will not be part of the CSR stat package.

18. LAYOUT SPECIFICATIONS FOR TABLES, LISTINGS AND FIGURES

All TFL is to include the following header:

GVGH	Vaccine: 1790GAHB
Final Report: Study H03_04TP	Two Doses in Healthy Adults

In all tables, listings and graphs investigational 1790GAHB vaccine groups will be labeled as

Group	Description	Label
A	1790GAHB with 25 µg of GMMA total protein	25mcg_Shi
B	1790GAHB with 100 µg of GMMA total protein	100mcg_Shi
C	control group receiving one dose of Menveo as 1 st injection and one dose of Boostrix as 2 nd injection	Control

For the mock-up catalogue to be used during programming, please refer to the document stored in within the SAS Drug Development (SDD) server.

Since all TFLs will be produced using SAS, the output actually generated may slightly differ from the mock-ups presented in the study specific Mock-up catalogue.

